6 STUDY SETTING

As the majority of acutely ill children are seen out of hospital by general practitioners and community paediatricians, the study will be conducted in 122 primary care or community paediatric practices throughout Belgium. The participating practices will be recruited by the academic centres for Primary Care of the KU Leuven, UGent, UAntwerpen, Université Liège, UCL and VUB (Brussels).

7 ELIGIBILITY CRITERIA

7.1 Inclusion criteria for practices

Practices' eligibility (and physicians within these practices) for inclusion in the study will be based on the following criteria:

- Being able to recruit acutely ill children (ideally consecutively)
- Agree to the terms of the clinical study agreement.

7.2 Exclusion criteria for physicians

Practices will be excluded from study participation based on the following criteria:

Currently using a POC CRP device as part of their routine care

No practices will be excluded on other grounds than the above. Age, demographics, geographic region will not be used to exclude eligible practices. This will provide us with a real-life, representative subset of ambulatory care physicians.

7.3 Inclusion criteria for children

Patients' eligibility for inclusion in the study will be based on the following criteria:

- Children aged 6 months to 12 years, provided informed consent can be obtained
- presenting with an acute illness episode that started maximum 10 days before the index consultation

7.4 Exclusion criteria for children

Patients will be excluded from study participation based on the following criteria:

- Children who were previously included in this trial
- children with an underlying known chronic condition (e.g. asthma, immune deficiency)
- clinically unstable warranting immediate care
- immunosuppressant medication taken in the previous 30 days
- trauma as the main presenting problem
- antibiotics taken in the previous 7 days
- Unwillingness or inability to provide informed consent

8 TRIAL PROCEDURES

8.1 Trial randomisation

In order to avoid contamination between physicians working in the same practice randomization will happen at the level of the general practice.

General practices and community paediatric centres will be randomized in one of the 2 study arms in a 1:1 ratio using a block randomization system stratified per recruiting academic centre in order to guarantee that allocation to either usual care or the intervention arm is balanced within every region.

Stratified block randomization will be done using an electronic random numbers generator in blocks of 4 practices. Randomisation and concealment will be centralised at the KU Leuven and conducted by a staff member not involved in data collection or delivering the intervention.

8.2 Blinding

Owing to study procedures, children, their parents and physicians will not be masked to the practices' random allocation.

8.3 Unblinding

Conditions and procedures for unblinding are not required as the participating physicians will be aware of their allocation.

8.4 Recruitment

Given the current special circumstances under the COVID-19 pandemic, we aim to recruit practices during two stages, with stage 1 acting as a run-in period before all practices will be asked to start recruiting patients. The first stage will allow the study team to recruit a smaller number of practices in a selection of the participating academic centres to further streamline the recruitment process and remedy any unforeseeable issues that might occur after the investigator meeting and study initiation. In a second stage more practices will be recruited both at the initial academic centres as well as the other participating academic centres. We aim to keep recruitment of practices as pragmatic as possible to limit the burden on practices dealing with the aftermath of the COVID-19 pandemic.

For the recruitment of general practices, each academic centre will regionally, according to their own customs for recruitment (and what training may be part of the recruitment process), approach physicians. A website with information about the trial could help the recruitment process. The website will contain a form, which can be completed by GPs. GP's can express their interest in the study without further obligations. The study teams of the

AC can contact the GP for a thorough explanation of the study, once approval of the ethics research committees is obtained. However, the information provided at the investigator meetings will be standardised and contain short and practical training on the new guidelines.

Both solo general practices and group practices are eligible for participation in the trial. Per general practice ideally only 1 or 2 physicians will be selected for participation in the study, in order not to dilute the number of patients per physician and thus to minimize the possibility of a strong selection of patients towards the most motivated - as perceived by the physician - and for practical reasons.

8.4.1 Patient identification

The participating physicians will be asked to (ideally) consecutively recruit children with an acute illness over the recruitment period covering two winter seasons.

Parents and children will be informed about the study by the physician. For that purpose, a patient information leaflet will be developed describing the aim and course of the trial and emphasizing the fact that it does allow the physician to overrule the clinical algorithm but aims to investigate whether the intervention may help reduce the antibiotic prescribing rate.

Parents and children willing to participate in the study will be asked to sign an informed consent form. Consent will be signed by the parents or legal guardian. We will include an age-adjusted assent procedure for older children (≥6 years).

8.4.2 Screening

The physician will assess eligibility and willingness to participate in the study. No additional procedures are required. The reasons for patient non-eligibility and non-participation - if provided - will be recorded in a designated screening log.

8.5 Consent

Eligible children (and their parents) will be informed by their physician about the study. Apart from a clear oral explanation, the parents will receive a comprehensive information leaflet.

All the information essential to the decision-making process of the participant will be provided including:

- a. a brief, clear presentation of the rights of the participant (voluntary participation and confidentiality)
- a clear description of the research project (context, objectives, inclusion/exclusion criteria, methodology & course) highlighting the constraints (point-if-care CRP testing) in addition to the standard treatment
- c. descriptions of the risks & benefits
- d. the right to withdraw from the study at any given point
- e. the approval of the ethical committee
- f. the researchers' contacts

Children and their parents will have the opportunity to ask questions about the study and sufficient time to make their decision. Children (and their parents) will be informed that they will still receive all the usual care, whether they choose to participate or not.

After that children and their parents will be asked officially to participate in the study. Consent will be signed by the parents or legal guardian. We will include an age-adjusted assent procedure for older children (≥6 years).

Some practices will be selected based on purposive sampling to take part in the nested qualitative study and will be provided with an additional sheet for the informed consent form to request permission from parents to be contacted by telephone (by a trained qualitative researcher of the study team) during follow-up to take part in a semi-structured interview.

8.6 Baseline data

At study entry, the following baseline data will be collected for each participating child:

age

gender

Data will be collected by the physician at the index consultation and entered in the eCRF.

8.7 Trial assessments

Assessment by physician

During the first consultation at baseline, a selection of **clinical features** will be assessed and recorded by the physician in the patient's health record and on the e-CRF, **including the clinical decision tree** (clinician's gut feeling, body temperature, dypnoea). **CRP testing** will be conducted as per the **diagnostic algorithm** as described above (See Flowchart).

The physician will be asked to note in the patient's health record and on the e-CRF whether antibiotics were prescribed, whether this was an immediate or delayed prescription. If the decision to prescribe antibiotics diverted from the suggested algorithm in the intervention arm, physicians will be asked to acknowledge this and explain why on the e-CRF.

Any additional care during follow-up will be left at the discretion of the child's physician. We will use a **point-of-care CRP** test which requires 1.5 μ I of capillary blood obtained by finger prick (results within 4 minutes). Clinical features will be recorded before the CRP test is conducted.

Follow-up (app)

Follow-up information for all children will be collected using direct patient/parent contact using a smartphone app. Information regarding the smartphone app as well as instructions on how to install will be handed to children and their parents at the baseline consultation.

The smartphone app will ask parents and/or children about daily symptoms such as body temperature, cough, treatment and whether they consulted a physician or went to the hospital. The daily follow-up will consist of a maximum of 10 short questions which are answered by ticking the appropriate box. Parents will be asked to complete these questions once a day until the symptoms have resolved and the child is considered cured of the acute illness.

Furthermore, the app will ask parents to complete a few quality-of-life items (proxy version of the EQ-5D-Y questionnaire)(24) and two pain scales (Wong Baker FACES Pain Scale, FLACC scale)(25,26) during follow-up. Some items will be requested daily (visual analogue scale of the proxy version of the EQ-5-D and the Wong Baker FACES Pain Scale), whereas other items will be presented weekly and/or until the child is feeling better (all items of the proxy version of the EQ-5D-Y and the FLACC scale). We will ask parents to complete these questions.

Follow-up (patient health record)

Follow-up information for all children will be collected from the patient health record up to 30 days after the index consultation. This information will be collected by the participating GP (follow-up form in the eCRF will be due 30 days after the index consultation) with or without support of a flying nurse during on-site visits after blocks of patients included. Follow-up information will consist of: diagnosis of a serious infection, re-attendance visits, medication prescribed, use of additional tests, admission to hospital, death, prioritizing the data related to safety events (mortality, admission to hospital, detection of a serious infection) as these would need to be assessed first in the eCRF, allowing appropriate safety measures to be put in place.

Interviews as part of the nested qualitative study

Individual telephone interviews will be conducted with a small selection of clinicians (approximately 16) and a selection of parents (approximately 14 to 18) taking part in the trial (nested qualitative study), to explore the social processes influencing embedding of the intervention within practice, and behaviour change techniques.

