KCE shall have the right (but not the obligation) to be present at each TSC meeting (more details can be found in the research agreement template).

The TSC will meet on average 3 times per year the first year and twice a year after that. The TSC is composed of the CI, the trial statistician, the trial PM, a representative of other participating centres or groups, up to 2 patients or members of the public, 1 representative of the sponsor, 1 representative of the funder.

The day-to-day management of the study will be performed by the Trial Management Group (TMG) which is distinct from the TSC and consists of the chief investigator and the trial coordinators.

TRIAL FLOW CHART

Figure 1 Flow chart ARON project

Figure 2 intervention arm: detailed flowchart

🖄 : decision tree, 🌢 : point-of-care CRP test, 🏊 : antibiotic treatment, 🦄 : safety netting advice, 🎹 : additional testing, H: referral to secondary care

Figure 2 describes the different steps of the diagnostic algorithm. First of all, the decision tree will be applied, if yes to any of three features (gut-feeling, dyspnea, temperature >40°C), physicians are advised to perform a point-of-care CRP test. If the CRP level is then 5 mg/L or above: referral or additional testing is advised to rule out a potential serious infection. If all features of the decision tree are reassuring (no to all) and a physician is still considering prescribing antibiotics, we advise them to perform a point-of-care CRP test and only consider prescribing if the CRP level is 5 mg/L or above. For example, in a child with dyspnee and a CRP level of <5mg/L, physicians are advised to prescribe antibiotics only if according to the prescribing guidelines.

Figure 3 control arm: detailed flowchart

. U: clinical assessment, ♥: clinical management, ♥: antibiotic treatment

(*) G	uidance on antibiotic prescribing (BAPCOC guide (November 2019) + RIZIV consensu	s meeting)
Preliminary diagnosis	Required criteria for rational antibiotics prescribing or referral	1 st choice AB treatmen
Bronchiolitis	Antibiotics: not indicated Referral: clinical deterioration; <3 months; breathing rate >60/'; reduced intake	none

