4.3 Primary endpoint

The primary outcome is the proportion of subjects who were prescribed antibiotic treatment (both immediate and delayed) at the index consultation as recorded by the treating physician.

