9.2 Legal status of the intervention

The trial is being carried out under a Clinical Trial Authorisation (CTA). The POC CRP device is therefore only to be used by the named investigators, for the patients specified in this protocol, and within the trial.

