11.2 Planned recruitment rate

Our groups have successfully completed a range of trials in both children and adults with acute illnesses in primary care.

The same primary care network used in previous studies by the sponsors group will be used for recruitment, previously resulting in sample sizes of up to 8962 children.

The planned recruitment period will be 21 months. Taking into account an inclusion rate of 1 in 5 of all eligible children, we will include a total of 122 ambulatory care physicians.

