14 ETHICAL AND REGULATORY CONSIDERATIONS

14.1 Ethics Committee (EC) review & reports

The study will be conducted in compliance with the principles of the Declaration of Helsinki (current version), the principles of GCP and in accordance with all applicable regulatory requirements. This protocol, the informed consent forms and other related documents e.g. advertisements and physician information letters, will be submitted for review to the Research Ethics Committee (REC) and to the Sector Committee for Social Security and Health of the Privacy Commission.

Any subsequent protocol amendments will be submitted to the REC and Sector Committee for approval. No substantial amendment that require review by REC will be implemented until the REC grants a favourable opinion for the study.

The study can and will be conducted only on the basis of prior informed consent by the parents or legal guardian of the study participants, to participate in the study. Extensive discussion of risks and possible benefits of participation will be provided to the patients and/or their families. The participating physician shall obtain a signed informed consent form for all study participants prior to their enrolment and participation in the study in compliance with all

applicable laws, regulations and the approval of the (local) Ethics Committee, if required. The research facility shall retain such ICFs in accordance with the requirements of all applicable regulatory agencies and laws.

All correspondence with the REC shall be retained in the Trial Master File/Investigator Site File.

The Chief Investigator acknowledges that it is his responsibility to produce annual progress reports (APR) and he will do so by submitting to the REC within 30 days of the anniversary date on which the favourable opinion was given, and annually until the study is declared ended.

The Chief Investigator shall notify the REC of the end of the study. Should the study be ended prematurely, the Chief Investigator will notify the REC and include the reasons for the premature termination. The Chief Investigator will submit a final report with the results, including any publications/abstracts, to the REC.

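### No rule in the readable text settles eligibility and consent before the antibiotic decision, so inclusion can depend on the primary outcome, probably more in the control arm

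*Protocol*

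**What the plan says.** Randomisation is by practice, and "children, their parents and physicians will not be masked to the practices' random allocation" (Protocol 8.2). The treating physician decides who enters: "The physician will assess eligibility and willingness to participate in the study. No additional procedures are required" (8.4.2). The same physician supplies the primary outcome, antibiotic prescription "at the index consultation as recorded by the treating physician" (4.3).

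Two rules fix an order of events:
- 8.7, on assessments: "Clinical features will be recorded before the CRP test is conducted".
- 14.1, on consent: "The participating physician shall obtain a signed informed consent form for all study participants prior to their enrolment and participation in the study".

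Section 8.5 adds that families are informed, given time, and then asked to take part. None of these mentions the antibiotic decision. The exclusion in 7.4 for recent antibiotic use concerns drugs already taken, not a prescription decided at the index visit.

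In the intervention arm, 9.2 says that the CRP device is "only to be used by the named investigators, for the patients specified in this protocol, and within the trial". The text under Figure 2 describes when a child with a negative decision tree is tested: if "a physician is still considering prescribing antibiotics, we advise them to perform a point-of-care CRP test". Control physicians give usual care and receive no extra tools (section 9).

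Consecutive recruitment is requested as an ideal (8.4.1), and the recruitment plan reads "Taking into account an inclusion rate of 1 in 5 of all eligible children" (11.2). Section 11.1.2 of the Protocol and the primary endpoint section of the SAP both name selection by expected antibiotic need as a threat and give criteria for suspecting it.

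**The concern.** A physician who knows the allocation can complete the clinical part of the visit, decide on antibiotics, and only then choose whether to invite the child. Doing so breaches neither ordering rule, provided consent is signed before enrolment. Inclusion would then be conditional on the primary outcome.

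The opening is probably wider in the control arm. An intervention child who gets a CRP test must already be a trial patient (9.2 with 14.1), so inclusion comes before the final prescribing decision. A control child has no such step. Intervention children who get no CRP test can also be enrolled late, so that arm is not closed to the problem.

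If outcome-dependent inclusion differs between arms, the treatment odds ratio is biased directly. The practice random effect and the age term in the SAP model do not remove this, because the shift is aligned with arm.

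**Working it through.** **Inputs from the documents.** Control rate 20.65%, intervention rate 14.35%, 50 children per cluster, ICC 0.063, two-sided alpha 0.05, power 0.90 (sample-size command, Protocol 11.1.2 and SAP). Overall observed rate 18% in the first 4938 children (same sections).

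**Reproducing the plan's figure.**
- Design effect = 1 + 49 × 0.063 = 4.087.
- Variance term = 0.2065 × 0.7935 + 0.1435 × 0.8565 = 0.2868.
- Clusters per arm = (1.960 + 1.282)² × 0.2868 × 4.087 / (50 × 0.063²) = 62.05, rounded up to 63. Using t quantiles gives 63.05.
- 2 × 63 × 50 = 6300, and 6300 / 0.9 = 7000. Both match the plan.
- Effective sample size per arm = 3150 / 4.087 = 770.7.

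The calculation uses a difference of 6.3 points. The accompanying text says 5.3. That is a separate discrepancy; 6.3 is used here because the 63 clusters rest on it.

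**Selection model (assumption).** Control physicians enrol children given antibiotics s times as readily as the others, and the intervention arm is unselected. The observed control rate is q = s·p / (s·p + 1 − p), so the observed odds are s times the true odds. The documents give no value for s.

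*No true effect, p = 0.18 in both arms, s = 1.2.* q = 0.216 / (0.216 + 0.82) = 0.2085, a false difference of 2.85 points. SE = √[(0.2085 × 0.7915 + 0.18 × 0.82) / 770.7] = 0.0201. z = 1.415. The chance of a significant result favouring the intervention is Φ(1.415 − 1.96) = 0.29, against 0.025.

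*Planned effect true, s = 0.8.* q = 0.1652 / (0.1652 + 0.7935) = 0.1723, an observed difference of 2.88 points. SE = 0.0186, z = 1.553, power = Φ(1.553 − 1.96) = 0.34, against 0.90.

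**Range at 63 × 50 per arm.**

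| s in control arm | No true effect: false difference | Chance of false benefit |
|---|---|---|
| 1.1 | 1.5 points | 11% |
| 1.2 | 2.9 points | 29% |
| 1.3 | 4.2 points | 54% |
| 1.5 | 6.8 points | 90% |

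| s in control arm | Planned effect: observed difference | Power |
|---|---|---|
| 1.0 | 6.3 points | 0.90 |
| 0.9 | 4.6 points | 0.69 |
| 0.8 | 2.9 points | 0.34 |
| 0.7 | 1.1 points | 0.08 |

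If the same s applied in both arms, both odds would be multiplied alike and the odds ratio would not move. Only the difference in selection between arms causes bias.

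**The triggers in Protocol 11.1.2 and the SAP.**
- The antibiotic trigger looks for physicians with more than 90% of children not needing antibiotics. No trigger looks for preferential enrolment of children who do receive them.
- The SAP ties that trigger to a negative decision tree, not to the prescription.
- The trigger of CRP testing in more than 90% of children can in practice apply only to intervention practices: 7.2 excludes practices already using a device, and 9.2 confines the trial device to the trial. The per-protocol set is therefore filtered unequally by arm.

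**The case against.** **The plan does more than discard extreme recruiters.** A reader might infer that dropping physicians beyond 90% is the only safeguard. It is not. Section 8.4 limits participation to one or two physicians per practice, partly to reduce selection, and standardises the investigator meetings; 8.4.1 asks for consecutive recruitment. There is also a screening log, a practice audit, monitoring visits, interviews, a trigger for fewer than 10 patients per year, baseline tests for recruitment bias (Protocol 11.3.1) and a per-protocol analysis. This stands. Beyond the first two, however, these measures detect or analyse selection; they do not prevent it.

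**The 90% rule is not blind to moderate selection.** It works per physician, so an arm average below 90% does not show that nobody is flagged. With a beta-binomial at ICC 0.063 and 50 children per practice, about 28% of control practices would have more than 90% of children without antibiotics if selection of s = 0.75 lowered the rate to 16.3%. With no selection, at 20.65%, the share is about 16%. So the rule responds, but it would also catch many unselected practices.

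**The CRP rule is not the only ordering rule, and the opening is not confined to control practices.** Both inferences are tempting, and the documents support neither. Section 14.1 is a second rule, and intervention children without a CRP test can be enrolled after the decision.

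**Evidence.** The values of s are hypothetical. An inclusion rate of one in five is a feasibility assumption and does not show outcome-dependent inclusion. Figures 1, 5 and 6 are not shown and the Trial Monitoring Plan is a separate document; either could state an order.

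**Timing of a remedy.** With 4938 children recruited at the amendment and REDCap data expected on 29/03/2024 (SAP), new eligibility wording may reach few children. Save order in REDCap is also an imperfect guide to when a decision was made. Both points stand and limit the fix.

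**Conclusion.** The point holds in this form: the readable text has no rule, in either arm, that eligibility and consent come before the antibiotic decision. With unmasked physicians and recruitment that is only ideally consecutive, inclusion can depend on the primary outcome, probably more in the control arm. The plan recognises the threat but mostly addresses it afterwards, with triggers that run in one direction or in practice reach one arm.

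Modest differential selection would matter: about 29% false benefit at s = 1.2, and power of about 0.34 at s = 0.8. These figures assume selection in the control arm only, the planning ICC and 63 clusters of 50 per arm. They illustrate sensitivity and do not estimate bias that has occurred. A reader might infer that the trial's result is biased in a known direction; the documents support neither the direction nor the amount. The sample-size arithmetic itself reproduces.

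**What to change.** **For children still to be recruited, both arms (Protocol 8.4.2 and 8.5).** State that eligibility and consent are completed, and the inclusion page saved in the eCRF, before the antibiotic decision, and that a child whose decision has already been made is not enrolled. Lock the prescription field until inclusion is saved. Do not require control physicians to enter the decision-tree items before prescribing, because that could bring part of the intervention into usual care.

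**For all children (SAP, before analysis).** Report inclusion, non-eligibility and non-participation from the screening log by arm. Add a supportive sensitivity analysis limited to records where inclusion was saved before the prescription, and state that entry time is an imperfect proxy for decision time.

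**Cost.** A short protocol addition, a form-order setting, one table and one analysis. The planned sample size does not change. Some late enrolments are lost, and the sensitivity set is smaller because records entered retrospectively may drop out.
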